7. ADVERSE EVENTS AND REPORTING PROCEDURES

7.1 Potential Adverse Events

The primary safety outcome is bleeding during the treatment period or until 2 days after the last dose of the study medication was administered (Lassen et al. NEJM 2020;26:2487-2498). Bleeding is categorized as major, clinically relevant nonmajor, or minor bleeding and as the composite of major and clinically relevant nonmajor bleeding. The definition of major bleeding is acute, clinically overt bleeding accompanied by one or more of the following findings: a decrease in the hemoglobin level of 2 g per deciliter or more over a 24-hour period; transfusion of 2 or more units of packed red cells; bleeding at a critical site (including intracranial, intraspinal, intraocular, pericardial, and retroperitoneal bleeding); bleeding into the operated joint, necessitating reoperation or intervention; intramuscular bleeding with the compartment syndrome; or fatal bleeding. Clinically relevant nonmajor bleeding includes acute, clinically overt episodes such as wound hematoma, bruising or ecchymosis, gastrointestinal bleeding, hemoptysis, hematuria, or epistaxis that does not meet the criteria for major bleeding. Bleeding is categorized as minor if it is clinically overt but is not adjudicated as major or clinically relevant nonmajor bleeding.

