11. STATISTICAL CONSIDERATIONS

11.1 Statistical Design

The primary study outcome is defined as overall bleeding event risk 90 days post-randomization. Secondary patient-oriented outcomes include risk of VTE events. Tertiary outcomes include: length of stay, location of patient on day 90 of follow up (home vs. SNF, etc), and clinically significant wound complications (infection, dehiscence, flap loss).

Process measures to be collected include time to starting anticoagulation after completion of skin closure, number of days patients received anticoagulation treatment, and timing of phone interview follow up.

Conservative estimates from recent retrospective study in over 1500 patients who underwent body contouring procedures (LMWH [N=454]; rivaroxaban [N=703], apixaban [N=415]) are used for our power analysis (37). Using standard formulas, with 80% power to detect a non-inferiority margin of -0.075, and assuming a 1.32% baseline in bleeding events among patients dosed on daily enoxaparin compared with a 1.73% rate of bleeding in direct oral anticoagulant (DOAC) arm patients over 90 days, our analysis expects enrollment size of 37 patients per arm. We conservatively estimate a 25% dropout rate over the course of the study, which results in a sample size of 100 (50 patients per arm).

The primary conclusions of this project will be analyzed based on intention-to-treat where all randomized patients will be analyzed within the groups they were originally allocated to. Two-sided 5% significance levels will be used to identify statistically significant results. Unadjusted analysis of the bleeding risk in apixaban use will be assessed using an exact Pearson chi-squared test. The outcome will be reported as an odds ratio with 95% confidence intervals. Baseline prognostic variables including age, BMI, Caprini score, Elixhauser comorbidity index score, procedure duration, unilateral vs. bilateral will be ascertained upon enrollment and reported by our study group. A subsequent covariate adjusted analysis will be undertaken with an adjusted logistic regression model.

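### The trial is sized on a 7.5-point non-inferiority margin, but the planned primary test is a two-sided test of no difference and nothing is compared with the margin

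*Combined protocol and SAP*

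**What the plan says.** Sections 9.1, 11.1 and 11.4 of the combined protocol and SAP carry the same text. The sizing sentence works "with 80% power to detect a non-inferiority margin of -0.075". It takes bleeding to be 1.32% on enoxaparin and 1.73% in the oral anticoagulant arm over 90 days. It concludes that "our analysis expects enrollment size of 37 patients per arm", which a 25% dropout allowance raises to 50 per arm and 100 in total.

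The next paragraph gives the analysis, by intention to treat in all randomized patients:

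- The unadjusted comparison is specified as follows: "Unadjusted analysis of the bleeding risk in apixaban use will be assessed using an exact Pearson chi-squared test".
- The error level is set for all tests together: "Two-sided 5% significance levels will be used to identify statistically significant results".
- The effect measure is an odds ratio, with a 95% interval.

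An adjusted logistic regression follows. Non-inferiority is mentioned only in the sizing sentence. Section 1.1 says only that bleeding rates will be examined. No section gives a non-inferiority hypothesis, an interval for the risk difference, a margin on the odds-ratio scale, or a rule linking any limit to 0.075. The alpha used for sizing is not stated.

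**The concern.** The sample size and the analysis address different hypotheses. Sizing supposes that the trial will rule out an excess of 7.5 percentage points or more. The chi-squared test asks whether the two risks differ at all. Failing to reject equality does not show that the excess is below 7.5 points, and with few events such a failure is the expected result almost whatever the truth.

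The odds-ratio interval does not fill the gap, because 7.5 points has no single odds-ratio equivalent; it depends on the enoxaparin rate.

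Bleeding is the primary outcome and a safety question. The risk is that a non-significant p-value is reported as similar bleeding when the data are compatible with an excess well beyond the margin. If the interval method, confidence level and direction are chosen after the counts are known, the choice can decide the conclusion.

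**Working it through.** **Inputs (section 11.1).** Enoxaparin rate pE = 0.0132; apixaban rate pA = 0.0173; margin 0.075 in size; power 80%; 37 per arm before dropout, 50 after. Bleeding is harmful, so the margin is taken as an apixaban excess of +0.075. If all randomized patients are analysed, n is 50 per arm; if the assumed dropouts are not analysed, it is 37.

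**1. Reproducing the plan's sample size.**

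n = (z_α + z_0.80)² × [pA(1−pA) + pE(1−pE)] / (0.075 − (pA − pE))²

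- Variance term: 0.0173 × 0.9827 + 0.0132 × 0.9868 = 0.03003.
- Distance to the margin: 0.075 − 0.0041 = 0.0709.
- One-sided 5%: 6.183 × 0.03003 / 0.0709² = 36.9, so 37 per arm. This matches, and 37/0.75 = 49.3 gives 50.
- One-sided 2.5% (a two-sided 95% limit): 7.849 × 0.03003 / 0.0709² = 46.9, so 47 per arm.

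The stated size is therefore a non-inferiority calculation. It fits one-sided 5%, not the two-sided 5% level and 95% interval of the analysis paragraph.

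**2. The margin as an odds ratio.** [(pE + 0.075)/(1 − pE − 0.075)] / [pE/(1 − pE)] is 7.2 at pE = 1.32%, 2.7 at 5% and 1.9 at 10%. The rates of 5% and 10% are assumptions.

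**3. What the planned test does.** All pairs of binomial counts were enumerated with the two-sided Fisher test. With equal arms this gives the same p-value as the conditional exact Pearson test. Probability of a non-significant result with enoxaparin at 1.32%:

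| True apixaban rate | 37 per arm | 50 per arm |
|---|---|---|
| 1.73% (planning rate) | >99.9% | >99.9% |
| 8.82% (+7.5 points) | 93% | 83% |
| 16.32% (+15 points) | 56% | 33% |
| 21.32% (+20 points) | 30% | 12% |

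The 1.32% comes from body contouring patients. Section 7.1 uses a broad definition ("Clinically relevant nonmajor bleeding includes acute, clinically overt episodes such as wound hematoma, bruising or ecchymosis"), so the trial's own rate may be higher. Probability of a non-significant result exactly at the margin, for other assumed enoxaparin rates:

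| Enoxaparin rate | 37 per arm | 50 per arm |
|---|---|---|
| 3% | 92% | 85% |
| 5% | 92% | 86% |
| 10% | 91% | 88% |
| 15% | 92% | 89% |
| 20% | 93% | 90% |

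**4. One possible result.** With 4 v 1 bleeds (apixaban v enoxaparin) at 50 per arm, the observed excess is 6 points and p = 0.36. The Newcombe 95% upper limit for the excess is 17.0 points, more than twice the margin.

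**5. Power of a rule that does use the margin.** Exact probability that the upper limit is below 0.075, Newcombe interval (Miettinen-Nurminen agrees at the planning rates):

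| True rates (enoxaparin v apixaban) | 90% interval, 37 / 50 per arm | 95% interval, 37 / 50 per arm |
|---|---|---|
| 1.32% v 1.73% | 55% / 60% | 21% / 47% |
| 5% v 5% (assumed) | 35% / 44% | 22% / 30% |
| 10% v 10% (assumed) | 27% / 33% | 16% / 20% |

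With a 95% interval at 37 per arm, even 0 v 0 bleeds fails (upper limit 9.4 points). At 50 per arm, 0 v 0 passes (7.1) but 1 v 1 fails (8.7). The formula in step 1 is optimistic because fewer than one bleed is expected per arm (50 × 0.0132 = 0.66; 50 × 0.0173 = 0.87).

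**The case against.** The strongest reply is that the plan reports an odds ratio with a 95% interval as well as a p-value. In the 4 v 1 example that interval is about 0.46 to 39.5 (Wald), so a careful reader would see the imprecision. The objective is only to examine rates, section 2.4 does not label the trial non-inferiority, and nothing says that non-significance will be read as similarity. This stands in part: the misreading is a risk, not something the plan commits to. But a wide odds-ratio interval is not a decision rule, and if non-inferiority is not intended, the margin and the 80% power have no function.

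Three narrower points:

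- **Alpha.** One-sided 5% is inferred. One-sided 2.5% with the 0.41-point difference taken in apixaban's favour gives 7.849 × 0.03003 / 0.0791² = 37.7, close to 37. That takes the difference in the wrong direction, though the negative sign on the margin makes such a slip conceivable. It strengthens the case for stating direction and alpha.
- **Power.** The loss applies to score-type limits. A simple Wald 90% interval keeps 87% (37 per arm) or 81% (50), but its type I error at the margin is 15% or 7.5% against a nominal 5%.
- **Inputs.** Non-significance at the planning rates is what any equality test gives when rates are nearly equal, so the rows at and beyond the margin carry the argument. The higher enoxaparin rates are assumptions, and section 7.1 uses a different time window from the 90-day primary outcome.

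**Conclusion.** The concern holds, and the plan should be corrected before any comparison of the arms. Followed as written, it cannot deliver a non-inferiority conclusion, and its 80% power does not describe the test it names. The planned test misses a margin-sized excess in 83% to 90% of trials at 50 analysed per arm and 91% to 93% at 37, for enoxaparin rates from 1.32% to 20%. The conclusion therefore does not hinge on the 1.32% figure. It assumes independent binomial counts, a 5% two-sided exact test, and a margin meant as an absolute apixaban excess. The counts needed will be collected; the decision rule is what is missing.

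**What to change.** In sections 9.1, 11.1 and 11.4:

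1. State H0: p(apixaban) − p(enoxaparin) ≥ +0.075 against H1: < +0.075, with a positive sign because bleeding is harmful.
2. Make the primary analysis the risk difference with a named score-type interval (Miettinen-Nurminen or Newcombe). Declare non-inferiority only if the upper limit is below +0.075.
3. State the alpha. One-sided 5% (two-sided 90% interval) matches the stated 37 per arm; one-sided 2.5% (two-sided 95% interval) matches the stated two-sided 5% level.
4. Restate power by exact enumeration for the chosen limit, at 1.32% and at higher enoxaparin rates.
5. Keep the exact chi-squared test and the odds ratio as descriptive, and say that a non-significant p-value is not evidence of non-inferiority.

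If the sponsor does not intend a non-inferiority claim, the consistent alternative is to remove the margin and its power statement and present the trial as estimating the risk difference.

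**Cost.** The change is to text only, and total enrolment can stay at 100, with the lower power in step 5 of the working declared. Keeping 80% power with a 95% limit needs a larger trial. The plan's formula gives 47 per arm (47/0.75 = 62.7, so 63 enrolled per arm, 126 in total), but that should not be adopted as sufficient: exact power is 25% with 47 analysed per arm and 55% with 63. With 100 analysed per arm it is 82%; at 25% dropout this means 100/0.75 = 133.3, so 134 enrolled per arm and 268 in total.

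### The trial is sized for non-inferiority on a risk difference but analysed with a test of no difference and an odds ratio; at its own planning rates that odds ratio often has no finite value

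*Combined protocol and SAP*

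**What the plan says.** Section 11.1 (Statistical Design) gives the whole statistical plan. Sections 9.1 and 11.4 repeat it.

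- Outcome: "The primary study outcome is defined as overall bleeding event risk 90 days post-randomization".
- Sizing: "Using standard formulas, with 80% power to detect a non-inferiority margin of -0.075", with bleeding rates of 1.32% (enoxaparin) and 1.73% (DOAC), and "our analysis expects enrollment size of 37 patients per arm". A 25% dropout allowance raises this to 50 per arm.
- Analysis: intention to treat, with an exact Pearson chi-squared test for the unadjusted comparison. "Two-sided 5% significance levels will be used to identify statistically significant results".
- Effect measure: "The outcome will be reported as an odds ratio with 95% confidence intervals".
- Adjusted analysis: "A subsequent covariate adjusted analysis will be undertaken with an adjusted logistic regression model".

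None of the three sections plans a risk difference, compares a confidence limit with 0.075, gives a margin for the odds ratio, or says what is reported when an arm has no events.

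**The concern.** There are two problems, and the first does not depend on how common bleeding is.

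1. **The analysis does not address the question used to size the trial.** The sizing asks whether apixaban adds less than 7.5 percentage points of bleeding. The chi-squared test asks whether the two rates are equal, and failing to reject equality in a small trial does not show non-inferiority. An odds ratio cannot be read against an absolute margin without also fixing a control rate.

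2. **The reported measure may not exist.** With so few expected events, an arm with none is likely at the planning rates. The ordinary odds ratio and the treatment coefficient of an ordinary logistic model then have no usable finite value on the log scale. With no rule in the plan, the interval method, measure or model would probably be chosen after the data are seen.

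**Working it through.** **Inputs (Section 11.1).** Enoxaparin 0.0132, apixaban 0.0173, margin 0.075, power 80%, 37 evaluable and 50 randomised per arm.

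**1. Reproducing 37 per arm.** Risk difference, unpooled variance:

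n = (z_α + z_0.80)² × [0.0132×0.9868 + 0.0173×0.9827] / (0.075 − 0.0041)²

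- The bracket is 0.03003 and the distance is 0.0709.
- One-sided 5%: 6.183 × 0.03003 / 0.005027 = 36.93, so 37. Then 37/0.75 = 49.3, so 50 per arm.
- One-sided 2.5%, which matches two-sided 5%: 46.88, so 47.
- The nearest alternative is one-sided 2.5% with the 0.41-point difference counted in apixaban's favour. It gives 38, but in the wrong direction for a harm.

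The margin is therefore an absolute risk difference. Its negative sign fits a calculation on the event-free proportion; for apixaban minus enoxaparin bleeding it is +0.075.

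**2. The odds ratio against the margin.** The odds ratio that corresponds to +7.5 points depends on the control rate:

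- 1.32%: (0.0882/0.9118)/(0.0132/0.9868) = 7.23
- 5% (assumed): (0.125/0.875)/(0.05/0.95) = 2.71
- 10% (assumed): (0.175/0.825)/(0.10/0.90) = 1.91

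**3. The test against the margin.** Suppose 5 of 50 bleed on apixaban and 0 of 50 on enoxaparin, an observed excess of 10 points. The exact two-sided p-value is 2 × C(50,5)/C(100,5) = 2 × 2,118,760/75,287,520 = 0.056. The difference is not significant, yet it lies beyond the margin.

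**4. Arms with no events, 50 per arm.** Expected events: 50×0.0132 + 50×0.0173 = 1.5.

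- P(none): enoxaparin 0.9868^50 = 0.515; apixaban 0.9827^50 = 0.418.
- At least one arm empty: 1 − 0.4854×0.5821 = 0.717.
- Split: odds ratio infinite 0.5146×0.5821 = 0.300; undefined 0.5146×0.4179 = 0.215; zero 0.4179×0.4854 = 0.203.
- At 37 per arm (0.612 and 0.524): 0.815.
- Assumed equal rates p, 1 − (1 − (1−p)^50)²: 0.389 at 3%, 0.148 at 5%, 0.010 at 10%.

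**5. What a risk difference would give.** Miettinen-Nurminen intervals in percentage points, with exact conditional odds-ratio intervals for comparison (50 per arm, apixaban v enoxaparin events):

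| Events | 95% score | 90% score | Exact 95% odds ratio |
|---|---|---|---|
| 0 v 0 | ±7.2 | ±5.2 | 0 to infinity |
| 1 v 0 | −5.3 to +10.6 | −3.2 to +8.5 | 0.026 to infinity |
| 1 v 1 | ±8.8 | ±6.8 | 0.012 to 80 |

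For 0 v 0 the limit d solves d/(1−d) = z²×2n/[n(2n−1)]. At n = 50 and 95%: 3.841×100/4,950 = 0.0776, so d = 7.2 points. At n = 37: 3.841×74/2,701 = 0.1052, so d = 9.5 points.

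**6. Chance that the score interval excludes +7.5 points.** Exact binomial sum at the planning rates:

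| Per arm | 95% interval | 90% interval |
|---|---|---|
| 50 | 47% | 60% |
| 37 | 21% | 55% |

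**The case against.** **The planning rates may be too low.** They come from a retrospective body-contouring series. Section 7.1 is broad: "Clinically relevant nonmajor bleeding includes acute, clinically overt episodes such as wound hematoma, bruising or ecchymosis", and it has a minor category as well. A reader might infer that the trial will lack a finite odds ratio in 72% of cases. The documents support that only conditionally: at 10% bleeding the problem almost vanishes. The scale mismatch remains at any rate.

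**Exact odds-ratio methods exist.** An exact conditional interval has an informative bound whenever at least one event occurs (1 − 0.215 = 78.5% of trials at the planning rates), and the exact test can also be run then. So it would be wrong to infer that no unadjusted result is possible. But the plan names no such interval, and at 1 v 0 events its upper limit is infinite.

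**The logistic model is a later analysis.** Its failure does not block the unadjusted result. Section 11.1 says "Baseline prognostic variables including age, BMI, Caprini score, Elixhauser comorbidity index score, procedure duration, unilateral vs. bilateral will be ascertained upon enrollment", which does not establish that all six enter the model.

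**The 80% can be recovered.** The 90% Wald interval matching the sizing formula excludes +7.5 points in 81% of trials at 50 per arm. That counts 0 v 0 tables, where the Wald interval has zero width. Without them it is 0.808 − 0.215 = 59%. A reader might blame the lower power on the change of measure, or on sample size alone. Neither is quite right: the gap appears when an interval suited to few events replaces a Wald-type formula that is unreliable at this size.

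**The margin might be read on the log-odds scale.** A reader might infer that a far larger trial is needed. The plan's own rates give a log odds ratio of ln(1.316) = 0.275 against apixaban, already beyond 0.075, so no size would suffice. Step 1 shows that this scale was not the one used.

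**Conclusion.** The concern holds. Following the plan as written leaves the non-inferiority question unanswered at any event rate. That part rests only on the reproduction of 37 per arm and on the absence of any decision rule tied to 0.075.

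The missing zero-event rule is a second, conditional problem. It affects 72% of trials at 50 per arm if 1.32% and 1.73% hold, and few if bleeding is near 10%. The documents do not settle the true rate.

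The stated 80% power does not carry over to a score interval. At 37 evaluable per arm and the 95% level, even a trial with no bleeding at all would miss the margin (±9.5 points). This should be corrected before data are seen. Confidence is moderate, because the zero-event and power figures depend on the planning rates.

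**What to change.** In Sections 9.1, 11.1 and 11.4:

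1. **Primary analysis.** Use the risk difference, apixaban minus enoxaparin, with a score interval such as Miettinen-Nurminen. Conclude non-inferiority only if the upper limit is below +0.075, and state the sign for a harmful event.
2. **Interval level.** State it. 95% matches the two-sided 5% in the plan; 90% matches the one-sided 5% behind the 37.
3. **Supportive analyses.** Keep the exact chi-squared test and the odds ratio as supportive, the latter with an exact conditional interval and reported as not estimable if there are no events.
4. **Adjusted model.** Label it supportive. Use a penalised fit (for example Firth) with few covariates named in advance, and only above a pre-stated minimum number of events. A zero-event rule alone is not enough. In simulations with six covariates unrelated to bleeding (an assumption), Firth odds ratios ran from 0.59 to 1.88 with no events, and from 0.60 to 7.29 at 1 v 0.
5. **Power.** Restate it for the level chosen, using the figures in step 6 of the working.

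The cost is wording in three duplicated sections, with no new data or visits. The restated power will be well below 80%. As a guide, a score-based (Farrington-Manning) sizing at the same inputs gives 77 evaluable per arm at one-sided 5%, or 100 at one-sided 2.5%. Whether to enlarge the trial or accept lower power is for the sponsor to decide and disclose.

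### At the planned bleeding rates (about 1.5 expected bleeds), an ordinary covariate-adjusted logistic model usually has no finite treatment odds ratio, and no sparse-event method is specified

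*Combined protocol and SAP*

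**What the plan says.** Section 11.1, repeated in 9.1 and 11.4, sizes the trial "assuming a 1.32% baseline in bleeding events among patients dosed on daily enoxaparin" and 1.73% for the apixaban (DOAC) arm. It takes 37 evaluable patients per arm and inflates for 25% dropout, "which results in a sample size of 100 (50 patients per arm").

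The primary conclusions rest on intention-to-treat and an unadjusted exact chi-squared test, with an odds ratio and 95% interval. The same paragraph then says: "Baseline prognostic variables including age, BMI, Caprini score, Elixhauser comorbidity index score, procedure duration, unilateral vs. bilateral will be ascertained upon enrollment"; it also promises to report them. The next sentence reads: "A subsequent covariate adjusted analysis will be undertaken with an adjusted logistic regression model".

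The plan does not say which of the six variables enter the model. It names no penalised or exact estimator, sets no limit on the number of terms relative to events, and does not say what will be reported if an arm has no bleeds.

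**The concern.** A logistic model fitted by maximum likelihood needs events on both sides of every binary term. If one arm has no bleeds, the treatment coefficient runs to plus or minus infinity. Software may then print a huge or near-zero odds ratio with a meaningless interval, or a convergence warning. If one laterality group has no bleeds, the laterality term fails in the same way. With about 1.5 bleeds expected, these are the usual outcomes at the planned rates.

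At stake is a committed second analysis of the primary outcome that will be read beside the main result. If it cannot be fitted, the team must choose another model or estimator after seeing the data, in an open-label trial. If it does converge, the interval is too wide to support or contradict anything.

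**Working it through.** **Inputs (section 11.1).** Enoxaparin rate 0.0132; apixaban (DOAC) rate 0.0173; margin 0.075; 80% power; 37 evaluable and 50 randomised per arm; six listed variables.

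**The plan's sample size.** n = (z_alpha + z_power)² × [p1(1−p1) + p2(1−p2)] / (margin − difference)². With one-sided 5%: (1.645 + 0.842)² × (0.01303 + 0.01700) / (0.075 − 0.0041)² = 6.18 × 0.03003 / 0.005027 = 36.9, so 37. Then 37 / 0.75 = 49.3, so 50 per arm. The stated figures reproduce, so these are the rates the plan was built on.

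**Expected bleeds.** 50 × 0.0132 + 50 × 0.0173 = 0.660 + 0.865 = 1.525. If arm and all six variables enter, that is 1.525 / 7 = 0.22 events per slope. P(no bleeds at all) = 21.5% and P(3 or fewer) = 93.3%.

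**Exact floor, arm term only.** P(no bleeds on enoxaparin) = 0.9868^50 = 0.515. P(no bleeds on apixaban) = 0.9827^50 = 0.418. P(some arm has none) = 0.515 + 0.418 − 0.215 = 0.717. This needs no assumption about covariates and holds for any ordinary logistic model that contains arm. With 37 per arm it is 81.5%.

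**Adding laterality.** A finite fit now needs a bleed in both arms and in both laterality groups. If laterality is split evenly and unrelated to bleeding (assumption), k bleeds fall in both groups with probability 1 − 2^(1−k).
- One bleed in each arm: P = 0.127, times 0.5 = 0.063.
- A 1-to-2 split between arms, either way: P = 0.096, times 0.75 = 0.072.
- Four or more bleeds with both arms represented: P = 0.283 − 0.127 − 0.096 = 0.060, times a factor between 0.875 and 1, so 0.052 to 0.060.

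The sum is 0.188 to 0.195, so about 81% have no finite estimate. With a 30:70 split the factors are 0.42, 0.63 and at least 0.75. The sum is then 0.159 to 0.174, so 83 to 84% fail. Simulation gave about 83%.

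**All six variables.** Simulation runs of 1,200 to 8,000 trials tested for separation by linear programming. Assumed distributions: age, BMI and duration normal; Caprini and Elixhauser counts or normal; laterality 50% or 30%. About 84% had no finite estimate. The range was 82 to 86% with covariates unrelated to bleeding, and 86 to 89% with prognostic covariates at the same overall event rate. With 37 per arm it was 89 to 91%.

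**Share with no finite estimate, by bleeding rate (50 per arm):**

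| Rates | Arm only (exact) | Arm + laterality (simulated) | Arm + all six (simulated) |
|---|---|---|---|
| 1.32% / 1.73% | 72% | about 83% | about 84% |
| 3% / 3% | 39% | 54% | 54–56% |
| 5% / 5% | 15% | 22–25% | 23–26% |
| 10% / 10% | 1% | 2% | 2–3% |

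Most of the failure is already present with arm alone, and laterality supplies nearly all the rest. The other five variables add a few points at most.

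**Precision when a fit exists.** For arm only, the 95% interval's upper limit divided by its lower limit is exp(2 × 1.96 × SE). With one bleed in each arm, SE = √(2 + 2/49) = 1.43 and the span is 270-fold. This is 0.127 / 0.283 = 45% of fits. With a 1-to-2 split, SE = √(1 + 1/49 + 1/2 + 1/48) = 1.24 and the span is 130-fold. This is a further 0.096 / 0.283 = 34%, so the median is 130-fold. With all six variables the simulated median is about 260- to 300-fold. At 5% per arm it goes from 39-fold to about 66-fold. The two medians come from different sets of trials, because the larger model converges less often.

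**The case against.** **The planning rates may be too low for this endpoint.** Section 7.1 classifies wound hematoma, bruising or ecchymosis, and minor bleeding as bleeding, and the primary outcome is overall bleeding risk. This stands: the failure rate is conditional on the rates and falls to 2 to 3% at 10% per arm. The documents give no rate for that definition in this surgery, so a higher rate is itself an assumption. The sponsor sized the trial on 1.32% and 1.73% and calls them conservative, so the analysis ought to be defined there.

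**The plan does not say that all six variables enter.** This also stands. Seven slopes is the natural reading of adjacent sentences but is not stated. The 72% floor does not depend on it. If fewer covariates were intended, they should be named.

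**A reader might infer that the fault is too many covariates and that a shorter model would cure it.** The figures do not support this: arm plus laterality fails about as often as arm plus all six. The extra covariates mainly cost precision, and intervals are already very wide without them.

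**A reader might infer that the primary analysis is invalid.** The documents do not support that either. The adjusted model follows an unadjusted exact test, and that test does not depend on it. The unadjusted odds ratio shares the 72% floor, but that is a separate matter.

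**Laterality and a risk difference are a matter of choice.** Fair. The documents do not show laterality to be the most prognostic of the six variables. What is needed is a method defined with zero events and a factor named in advance.

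**Conclusion.** The point holds for the adjusted analysis and is conditional on the planning rates. At 1.32% and 1.73% with 50 per arm, an ordinary logistic model has no finite treatment odds ratio in at least 72% of trials. The figure is about 83% with laterality and about 84% with all six variables. The first is exact; the other two rest on assumed covariate distributions. In the minority of trials that converge, the median 95% interval spans 130-fold with arm alone and up to about 300-fold with all six.

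The cause is the number of events, not mainly the number of covariates. At 5% per arm about 23% of trials still fail; at 10% the existence problem nearly disappears. The plan should be changed because it commits to this model in three places and provides no sparse-event method, but the primary test does not depend on it.

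**What to change.** In 9.1, 11.1 and 11.4, replace the ordinary adjusted logistic model with one pre-specified analysis that is defined when an arm has no bleeds. Either option would do:

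- A risk difference stratified on one named baseline factor the trial already records, for example unilateral versus bilateral, with a stratified Miettinen-Nurminen or stratified Newcombe interval and the stratum weights stated. This is on the same scale as the 0.075 margin.
- Firth-penalised logistic regression with arm and that one factor, if an odds ratio is preferred.

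Name the choice before any outcome data are reviewed, label it supportive, and say what will be reported if one or both arms have no bleeds. Report the remaining listed variables descriptively by arm. Shortening the covariate list while keeping ordinary maximum likelihood would not solve the problem.

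The cost is SAP wording only, with no new data, visits or patients. The other listed variables are no longer adjusted for. With zero or very few bleeds the Firth estimate is driven by its penalty, so a finite number should not be read as an informative one.
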